Protocol

Alcohol Metabolism and Disease Risk in Asians

NCT number NCT04967599

Document Date 08/08/2024

Protocol

This exploratory/developmental pilot study uses a parallel study design with a brief online behavioral intervention component. Participants are 360 college students of Asian heritage recruited as two cohorts, a group of incoming first year college students and a group of college students already on campus who report having flushed when they first started drinking alcohol. After a baseline assessment including surveys and DNA collection for genotyping, participants are randomized in equal numbers into one of three feedback groups (n = 120 per group) based on lifetime drinking (Incoming cohort only) and having an ALDH2*2 allele: 1) Phenotype only (PHEN): this intervention provides information on health-related risk associated with alcohol consumption and alcohol metabolism gene variations plus personalized feedback on flushing phenotype and associated risks; 2) Phenotype and Genotype (PHEN+GENE): the PHEN intervention plus personalized feedback on alcohol metabolism genotypes and associated health-related risks; or 3) CONTROL: an attention control session that does not provide feedback included in PHEN or GENE. Participants then are followed in four post-intervention behavioral surveys over 10 months and in the final 10-month follow-up also complete an evaluation of the study and retention of the intervention information. Our alcohol outcome measures include peak quantity (primary) and secondary measures of drinking frequency, weekend drinking, and total amount of drinking. Additional secondary outcome behaviors include percent of time used flush cures when drinking and transition to drinking in initial non-drinkers.

Data Analysis Plan

Alcohol Metabolism and Disease Risk in Asians

NCT number NCT04967599

Document Date 08/08/2024

Data Analysis Plan

We conduct nonparametric group comparisons to test for group differences among the three intervention groups in our primary and secondary outcomes. For outcomes that are continuous (alcohol consumption measures), we conduct the Kruskal-Wallis test. For the non-drinker and the flush cure use outcomes that are categorical, we conduct either the uncorrected chi-squared test when all of the expected cell counts are at least 5, or the Fisher's exact test when any of the expected cell count is less than 5. We adjust the p-value for significance to a more conservative value of <.01 to adjust for multiple comparisons.

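### The plan does not say what phenotype feedback lifetime non-drinkers receive, and the primary rank test ignores the drinking factor used in randomization, which can cost sensitivity

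*Combined protocol and SAP*

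**What the plan says.** The Protocol section describes the sample thus: "Participants are 360 college students of Asian heritage recruited as two cohorts". These are incoming first-year students and "college students already on campus who report having flushed when they first started drinking alcohol". Allocation is "randomized in equal numbers into one of three feedback groups (n = 120 per group") and is made "based on lifetime drinking (Incoming cohort only) and having an ALDH2*2 allele".

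PHEN has two parts. One is general: "this intervention provides information on health-related risk associated with alcohol consumption and alcohol metabolism gene variations". The other is personal: "plus personalized feedback on flushing phenotype and associated risks". PHEN+GENE adds genotype feedback, and CONTROL is an attention session with none of this feedback. Peak quantity is the primary outcome. One secondary outcome is "transition to drinking in initial non-drinkers".

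The Data Analysis Plan uses nonparametric comparisons to "test for group differences among the three intervention groups in our primary and secondary outcomes". The consumption measures get a Kruskal-Wallis test at p<.01. No stratification, restriction or subgroup by drinking status or cohort is stated.

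**The concern.** Two features of the plan do not fit together well.

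- **Content.** A student who has never drunk has no alcohol-flushing experience to report, and the plan names no other basis for assigning a phenotype. If no other basis exists, PHEN in this stratum is general information only, and PHEN+GENE is general information plus genotype. A PHEN result on transition to drinking, in either direction, could then be credited to phenotype feedback that these students did not receive.
- **Analysis.** Lifetime drinking is likely to be one of the strongest baseline predictors of peak quantity, because never-drinkers who stay abstinent score zero. The primary test ranks everyone together. It thereby puts a large, known source of variation into the noise, although the trial already uses that factor in randomization. A null primary result could partly reflect this choice rather than a failed intervention.

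**Working it through.** **1. What the documents establish.** Students in the campus cohort report flushing when they first drank, so all of them have drunk. Never-drinkers can therefore come only from the Incoming cohort. They are present there, because lifetime drinking enters the randomization and transition to drinking is an outcome. Cohort sizes and the never-drinker share f are not given. The method of determining flushing phenotype is not given either.

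**2. The plan's own figure.** 3 × 120 = 360, which reproduces. There is no power statement to reproduce, so everything below rests on assumptions.

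**3. Dilution by hand.** Assume a standardized effect d in drinkers, none in never-drinkers, and equal SD. The pooled effect is d(1 − f). For two arms of n = 120 at two-sided 0.01:

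power = Φ(d(1 − f)·√(n/2) − 2.576), with √60 = 7.746.

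For d = 0.5:
- f = 0: 0.50 × 7.746 − 2.576 = 1.297, power 90%
- f = 0.3: 0.35 × 7.746 − 2.576 = 0.135, power 55%
- f = 0.5: 0.25 × 7.746 − 2.576 = −0.640, power 26%

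**4. Simulation of the planned test.** Three-group Kruskal-Wallis at p<.01, 120 per arm, 2,000 to 3,000 trials per setting in most runs. Assumptions for drinkers: gamma-Poisson counts (shape 3), mean 5 in CONTROL and 3.5 in both feedback arms. Reference case for never-drinkers: 60% remain at zero, and the rest have mean 3 in every arm. The strong-effect case has 45% (CONTROL) v 70% (feedback arms) remaining at zero, and mean 3 v 2.1 drinks in those who start. Ranges are over repeated runs.

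| Test and effect in never-drinkers | f = 15% | f = 30% | f = 40% |
|---|---|---|---|
| Pooled, no effect | 0.57–0.58 | 0.22–0.26 | 0.11–0.12 |
| Pooled, uptake cut by a quarter | 0.62 | 0.38 | 0.24 |
| Pooled, uptake halved | 0.69 | 0.53 | 0.46 |
| Pooled, strong effect | 0.77–0.78 | 0.73–0.74 | 0.73–0.75 |
| Ever-drinkers only (any scenario) | 0.74–0.77 | 0.63–0.67 | 0.54–0.57 |

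With no never-drinkers, power is 0.83 to 0.85. At f = 30% the ever-drinker analysis has 120 × 0.7 = 84 per arm.

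**5. Rank test stratified by baseline drinking.** Participants are ranked within each stratum and the result is combined over strata. At f = 30% its power is about 0.47 with no effect in never-drinkers (pooled: 0.22 in the same run) and about 0.90 with the strong effect (pooled: 0.74). It beat the pooled test in every setting with never-drinkers that was compared.

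**6. Sensitivity to the drinker model.** With more dispersed counts and a smaller effect (mean 5 v 3.75), pooled power was 46%, 30%, 15% and 7% at f = 0, 10, 20 and 30%. The level changes, but the direction does not.

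**7. Transition outcome.** At f = 10% to 40% there are 120f = 12 to 48 never-drinkers per arm. An assumed 50% v 30% transition then has pairwise power of 5% to 28% at 0.01. The outcome is imprecise whatever the feedback contains.

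**The case against.** A reader might infer three stronger things: that non-drinkers have nothing that could be fed back to them, that the transition outcome therefore cannot test PHEN, and that the primary comparison is diluted as a matter of fact. The documents do not support any of these as stated.

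- The baseline is described as including surveys and DNA collection, which is not an exhaustive list. The flushing wording is the entry criterion of the other cohort. In a summary this brief, silence on intervention content is weak evidence that feedback was impossible.
- PHEN is a package. In non-drinkers it still differs from CONTROL by the general content, so transition to drinking is a valid randomized comparison of packages. What may be missing is only the phenotype component.
- Dilution requires little or no effect in never-drinkers. They do receive general information and, in PHEN+GENE, genotype feedback. They can start at different rates and reach different peaks, so they carry information. Under the strong-effect scenario, restricting to ever-drinkers loses power: about 0.66 against 0.74 at 30%.
- Restriction does not isolate phenotype feedback. PHEN and CONTROL also differ by general information in ever-drinkers, and no contrast in this design separates the two.
- Randomization uses lifetime drinking in the cohort concerned, so the arms should be balanced on it. The all-randomized analysis is legitimate, and this is a pilot.

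All five stand. They remove the case for replacing the primary comparison by an ever-drinker analysis. They do not answer the gap in stated content, or the omission from the test of a factor used in randomization. The advantage of stratification over pooling held in both the no-effect and the strong-effect scenario.

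**Conclusion.** The point holds in limited form. The plan leaves open what lifetime non-drinkers in PHEN are told about a phenotype that, on the only basis described, they have not experienced. Its primary test ignores lifetime drinking. The consequence is possible loss of sensitivity and a risk of misattribution, not bias.

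The loss cannot be given as one number. At an assumed 30% never-drinkers, the pooled test ranges from about 0.22 to 0.74 as the effect in never-drinkers goes from none to strong, while the stratified test goes from about 0.47 to 0.90. Which of the pooled and ever-drinker analyses is stronger depends on that effect. With none, ever-drinkers alone (about 0.65) also beat the stratified test; with a strong effect they are the weakest of the three. The never-drinker share, effect sizes, count distributions and uptake rates are all assumptions. The levels should not be read as estimates of this trial's power.

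**What to change.** 1. State how flushing phenotype is determined, and what a lifetime non-drinker in PHEN or PHEN+GENE receives under that label.
2. Keep the all-randomized peak-quantity comparison. Pre-specify a rank test stratified by baseline lifetime drinking, and report the result in baseline ever-drinkers of both cohorts beside it. Say in advance which result carries the primary claim, so that the additions do not give extra chances at p<.01.
3. Read PHEN versus CONTROL in ever-drinkers as the effect of the PHEN package including phenotype feedback, not of phenotype feedback alone.
4. If non-drinkers receive no phenotype feedback, read PHEN versus CONTROL on transition to drinking as general information and PHEN+GENE versus PHEN as genotype feedback. Draw no conclusion on phenotype feedback from that outcome. The Data Analysis Plan lists only three-group tests, so these pairwise contrasts need to be named.

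The cost is plan wording and one extra run on a factor already recorded for randomization. The ever-drinker result rests on a smaller sample, and the claim on transition becomes narrower.

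### Only three-group tests are planned, with no pairwise contrast or effect estimate, so a significant result cannot show whether the PHEN package works or genotype feedback adds to it

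*Combined protocol and SAP*

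**What the plan says.** The Protocol section defines three arms in steps.

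- **CONTROL** is "an attention control session that does not provide feedback included in PHEN or GENE".
- **PHEN** is the first step: "this intervention provides information on health-related risk associated with alcohol consumption and alcohol metabolism gene variations plus personalized feedback on flushing phenotype".
- **PHEN+GENE** is the second: "the PHEN intervention plus personalized feedback on alcohol metabolism genotypes and associated health-related risks".

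Participants total 360, with 120 per arm, followed in "four post-intervention behavioral surveys over 10 months". Peak quantity is primary. Three further drinking measures are secondary, as are "percent of time used flush cures when drinking and transition to drinking in initial non-drinkers".

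The Data Analysis Plan is one paragraph. Its aim is to "test for group differences among the three intervention groups in our primary and secondary outcomes". Drinking measures get a Kruskal-Wallis test. The two categorical outcomes get a chi-squared or Fisher test, depending on expected counts. On multiplicity it says only: "We adjust the p-value for significance to a more conservative value of <.01 to adjust for multiple comparisons". It gives no pair of arms, follow-up rule, direction, effect estimate or interval.

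**The concern.** A separate PHEN arm makes it possible to tell the effect of genotype feedback from the effect of everything else in the package. Two questions follow from the arm definitions: does the PHEN package beat control, and does genotype feedback add to it? The documents state no hypothesis, so these questions are inferred.

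The planned tests ask only whether the three groups differ somewhere. A significant result fits genotype feedback doing nothing, genotype feedback doing everything, or PHEN alone raising drinking. Without a prespecified contrast, the choice of pair is left until the data are seen. Without an estimate and interval, the pilot gives no planned effect size on which to base a next study.

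**Working it through.** **Figure to reproduce.** The documents give no power, effect size, SD, event rate or loss rate. The only arithmetic to check is 3 × 120 = 360, which agrees.

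**Why the three-group test cannot attribute an effect.** For arm sizes n_j, rank sums R_j and total N, the Kruskal-Wallis statistic is H = [12 / (N(N+1))] Σ R_j²/n_j − 3(N+1). H does not change if arm labels are swapped or the ranking is reversed. Write the means as (CONTROL, PHEN, PHEN+GENE). Reversing the sign of (0, 0, −.4) and subtracting .4 gives (−.4, −.4, 0), which is (0, −.4, −.4) with arms relabelled. Adding a constant to (0, +.4, 0) and relabelling gives the same pattern. With equal arms and a symmetric outcome, the test therefore has exactly the same power in all three situations.

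**Illustration by simulation.** From the documents: three arms, 120 per arm, the .01 level, the named tests and the expected-count rule. Everything else is assumed: effect sizes, distributions, 20% loss (120 × .8 = 96), category coding, and 60 or 40 per arm for the categorical outcomes. Those outcomes will have fewer than 120 analysed, because one is confined to initial non-drinkers and the other to drinking occasions; the documents do not say how many. A pair counts only if the three-group test is also significant. There were 20,000 runs for normal and binary outcomes and 10,000 for counts. In each cell the first figure is for genotype feedback adding nothing, the second for it being the whole effect.

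| Outcome (assumed) | Per arm | Three-group test, % | Gated PHEN+GENE vs PHEN, % |
|---|---|---|---|
| Normal, .4 SD | 120 | 72.1 / 72.5 | 1.1 / 62.2 |
| Normal, .4 SD | 96 | 58.8 / 59.2 | 1.0 / 48.5 |
| Negative binomial, mean 6 vs 3.5, size 1.5, 20% extra zeros | 120 | 57.6 / 59.7 | 0.9 / 47.7 |
| Same, 40% extra zeros | 120 | 20.5 / 19.8 | 0.7 / 13.4 |
| Binary, .50 vs .30 | 120 | 79.4 / 77.6 | 1.1 / 68.3 |
| Binary, .50 vs .30 | 60 | 40.3 / 37.9 | 0.9 / 29.6 |
| Binary, .50 vs .30 | 40 | 24.0 / 21.8 | 0.8 / 15.7 |
| Three categories, .30/.40/.30 vs .55/.30/.15 (chi-squared throughout) | 60 | 55.4 / 55.4 | 0.9 / 44.5 |
| Same | 40 | 31.9 / 33.0 | 0.8 / 23.9 |

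A separate 5,000-run simulation of the first row gave 71% and 71% for the three-group test, and 71% when PHEN alone raises drinking.

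**Formula check on the contrast.** For two groups of 120 and a .4 SD shift, z = .4/√(2/120) = 3.10. Power at two-sided .01 is Φ(3.10 − 2.576) = Φ(.52) ≈ .70. The rank-sum test without the gate gives 67%, and with it 62%.

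**Does the gate control error?** With three groups, if any two pairs are equal then all three are. So either all groups are equal, and the three-group test at .01 protects every pair, or at most one pair is equal, and that pair is itself tested at .01. In simulation with no effect, some gated pair was significant in 0.8% to 1.1% of trials across all settings.

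**Where that protection stops.** It covers one analysis of one outcome. If all four surveys are tested, independence gives 1 − .99⁴ = 3.9%. Simulation gave 4.1%, 3.4%, 2.9% and 2.1% at assumed between-survey correlations of 0, .5, .7 and .9. The plan does not say what its .01 covers. Six outcomes are listed: .05/6 = .0083, .05/5 = .01, and six independent tests at .01 give 1 − .99⁶ = 5.9%.

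**Limit on what contrasts can show.** With graded means (0, −.2, −.4) and 120 per arm, the three-group test is significant in 56% of trials, but each adjacent contrast in only 13–14%. Among significant three-group results, about 52% have neither adjacent pair below .01.

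**The case against.** The strongest reply is that readers see data as well as a p-value. Among significant three-group tests in the normal .4 SD scenarios, the PHEN median lay nearer PHEN+GENE than CONTROL in 94% of trials when genotype feedback adds nothing, and in 6% when it is the whole effect. Medians would often point the right way. That stands, and it lowers the weight. But medians split 51/49 in the graded case, and the plan commits to reporting none.

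The contrast of 1% with 62% is a valid test's error rate set beside its power at an assumed effect. It illustrates the gap and does not measure harm. Where both steps contribute, or the categorical outcomes are small, the contrasts have little power. This also stands, and it is a reason to report intervals.

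The Protocol opens with "This exploratory/developmental pilot study uses a parallel study design", and an omnibus screen is defensible in such a study. That limits severity, but a pilot's main product is estimates, and none is planned.

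The plan's mention of multiple comparisons might be meant to include pairs. It might equally mean outcomes. Every named test is applied to three groups and no follow-up rule is written, so this reading does not supply the missing contrasts.

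The gate is one choice among several and costs some power (67% to 62%). Testing the two adjacent contrasts directly would be a reasonable alternative.

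**Conclusion.** The concern holds. The plan as written supports no test or interval for the PHEN package against control, or for genotype feedback added to PHEN. That follows from the text and from the symmetry of the three-group test, and does not depend on the assumed effect sizes.

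The simulated percentages do depend on them and are illustrative. Across the assumed settings, the three-group test's rejection rates in the two opposite patterns differ by at most about 2 percentage points, while the gated genotype contrast separates them by amounts that vary with power (from 0.7 vs 13.4% to 1.1 vs 68.3%).

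The weight is moderate. This is an exploratory pilot with only three possible pairs and inferred questions, and the plan should be improved because the remedy is cheap.

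**What to change.** Prespecify three contrasts: PHEN vs CONTROL (the whole package), PHEN+GENE vs CONTROL, and PHEN+GENE vs PHEN (added genotype feedback).

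- **Testing.** For each outcome, at one named time point, if the three-group test is significant at .01, test each pair at .01. Use the rank-sum test for drinking measures, and chi-squared or Fisher under the plan's expected-count rule for categorical outcomes. No further penalty is needed within that outcome.
- **Multiplicity.** State what .01 covers. Handle testing across outcomes separately, and across surveys if more than one is tested.
- **Estimates.** Whatever the test result, report each contrast with a 95% interval. For drinking measures, give the probability of lower drinking and the difference in means; the two can disagree in skewed data. For binary outcomes, give the risk difference. If flush-cure use is coded in more than two categories, give differences in category proportions.
- **Labelling.** Call the intervals descriptive and unadjusted, and say that the gated tests govern claims of significance. This matters: in the normal scenarios at 120 per arm, some 95% interval (taken as rank-sum p < .05) excluded no effect while the gated tests declared nothing in 22–32% of trials, and in 11% with no effect. Intervals at 99% would reduce that conflict.

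The cost is a few lines and three rows per outcome, with no new data. Intervals will be wide. At 120 per arm the 95% half-width is 1.96√(2/120) = .25 SD. On the probability-of-lower-drinking scale it is 1.96√(241/(12 × 120²)) = .07, where a .4 SD shift is Φ(.4/√2) = .61. For .50 vs .30, the risk-difference half-width is 1.96√((.25 + .21)/60) = .17 at 60 per arm and .21 at 40.

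### The primary Kruskal-Wallis test on peak quantity ignores the factors used to randomize; it is valid but gives up power if those factors predict drinking

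*Combined protocol and SAP*

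**What the plan says.** The Protocol recruits two cohorts and states that "participants are randomized in equal numbers into one of three feedback groups", 120 per group, "based on lifetime drinking (Incoming cohort only) and having an ALDH2*2 allele". Genotype is known before allocation: "After a baseline assessment including surveys and DNA collection for genotyping". The outcomes are set out as follows: "Our alcohol outcome measures include peak quantity (primary) and secondary measures of drinking frequency, weekend drinking, and total amount of drinking". A separate secondary outcome covers "transition to drinking in initial non-drinkers".

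The Data Analysis Plan assigns the alcohol measures to one method: "For outcomes that are continuous (alcohol consumption measures), we conduct the Kruskal-Wallis test". On the threshold it says: "We adjust the p-value for significance to a more conservative value of <.01 to adjust for multiple comparisons". It names no stratum, covariate or baseline adjustment for any outcome. It also does not say whether initial non-drinkers enter the peak-quantity comparison.

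**The concern.** The design treats lifetime drinking and ALDH2*2 status as important enough to steer allocation, and then the primary test discards them. Kruskal-Wallis judges the differences between groups against the total variation in ranks. If part of that variation belongs to the strata, and the groups are balanced on the strata, that part cannot produce chance differences between groups, yet it still inflates the yardstick. The test is then stricter than its nominal .01. If the groups are not balanced on the strata, the size stays near .01, but stratum variation remains as noise that adjustment would remove.

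It is plausible that the factors matter here. Students who have never drunk would be expected to report low or zero peak quantity, and the trial's premise ties ALDH2*2 to the response to alcohol. With N fixed at 360 and a threshold already set deliberately low, an avoidable loss of sensitivity on the primary outcome deserves attention.

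**Working it through.** **Inputs from the documents.** Three equal groups of 120 (3 × 120 = 360, which agrees with the stated total); threshold .01; Kruskal-Wallis on 2 degrees of freedom, critical value 9.21. No power, effect size, SD or variance share is stated, so there is no planned power to reproduce.

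**Assumed inputs.** R², the share of rank variance explained by the strata: .1, .2, .3. One arm differs from the other two by d = .3, .4 or .5 SD. Taking lifetime drinking as yes/no gives six strata: Incoming by drinking by allele (4) and on-campus by allele (2).

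**Step 1: size under balanced allocation.** The null statistic is about (1 − R²) × χ²(2), so size = P(χ²(2) > 9.21/(1 − R²)) = .01^(1/(1−R²)). This gives .0060, .0032 and .0014.

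**Step 2: closed-form power under balanced allocation.** With one arm differing, λ = 360 × (2/9) × d² = 7.2, 12.8, 20.0. Kruskal-Wallis power is P(χ²(2; λ/(1−R²)) > 9.21/(1−R²)). Adjusted power is P(χ²(2; λ/(1−R²)) > 9.21).

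| d | R² = .1 | R² = .2 | R² = .3 |
|---|---|---|---|
| .3 | .420 vs .487 | .408 vs .553 | .393 vs .631 |
| .4 | .764 vs .812 | .772 vs .867 | .781 vs .916 |
| .5 | .950 vs .965 | .958 vs .982 | .967 vs .993 |

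(Kruskal-Wallis first, adjusted second, in this and the next table.)

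**Step 3: simulation.** The closed form treats ranks as fully efficient and so runs a few points high. Simulated power with a normal outcome, six strata of 60, 20,000 null runs and 5,000 effect runs:

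| d | Allocation | R² = .1 | R² = .2 | R² = .3 |
|---|---|---|---|---|
| .3 | balanced | .389 vs .461 | .371 vs .519 | .347 vs .590 |
| .3 | unstratified | .40 vs .45 | .39 vs .50 | .39 vs .58 |
| .4 | balanced | .731 vs .781 | .733 vs .842 | .724 vs .889 |
| .4 | unstratified | .72 vs .78 | .71 vs .83 | .71 vs .89 |
| .5 | balanced | .931 vs .952 | .939 vs .975 | .952 vs .990 |
| .5 | unstratified | .92 vs .95 | .92 vs .97 | .92 vs .99 |

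Kruskal-Wallis size was .0052, .0033 and .0017 when balanced, and .009 to .011 when unstratified. Rank ANCOVA stayed between .0093 and .0111 throughout. At R² = 0 the two tests agree (d = .4: .721 vs .725), so adjusting costs essentially nothing when the factors are irrelevant.

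A second simulation used skewed integer outcomes with ties, permuted blocks of 3 within six equal strata, and 20,000 runs. At R² of about .11 and .32, Kruskal-Wallis size was .0059 and .0010. Power was 59.7% vs 65.5% and 40.0% vs 65.3% for a stratified rank test. With no stratum effect both had 66.1%.

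**Step 4: sample-size equivalent.** Under unstratified allocation, adjusting is worth N = 360/(1 − R²) = 400, 450 or 514. Under balanced allocation, at 80% power, the equivalents are about 394, 436 and 489.

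**Step 5: who is analysed.** Zero-inflated Poisson-lognormal counts (log SD .7), strata of 45, 45, 45, 45, 60 and 120, balanced allocation, one arm with a 40% lower mean:

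| R², all 360 | KW vs adjusted, all 360 | R², non-drinkers excluded (n = 270) | KW vs adjusted, n = 270 |
|---|---|---|---|
| .25 | .27 vs .43 | .05 | .47 vs .49 |
| .12 | .30 vs .37 | .03 | .37 vs .39 |
| .03 | .41 vs .42 | .02 | .31 vs .31 |

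Much of the gain comes from separating initial non-drinkers from drinkers.

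**The case against.** The strongest reply is that nothing here is wrong. The test is valid, no stated figure is contradicted, and the Protocol calls the trial an exploratory pilot with no power target, so no planned power is missed. The loss is also relative. In the closed form at d = .4, Kruskal-Wallis has .757 at R² = 0 and .764 to .781 at R² = .1 to .3, so it misses a gain but does not fall below that mark. An absolute fall appears only at d = .3 (.431 to .393). Every R² and effect is assumed, and the gain runs from about zero to 24 points. Finally, the analysis population may matter more than adjustment: in the first row of the last table, plain Kruskal-Wallis without initial non-drinkers (.47) beats the adjusted test on everyone (.43).

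All of that stands as a limit on the size of the point. None of it removes the point. Pilot status does not make unused information less useful when N is fixed and the threshold is strict. The gain appears under both readings of the allocation, and adjustment costs nothing measurable when the factors are uninformative. The population point is a second thing for the plan to settle, and not a reason to ignore the strata.

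**Conclusion.** The concern holds as a matter of efficiency, not of bias or validity. No randomization factor enters the primary test.

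- If allocation was balanced on the factors and they predict peak quantity, the true size is below .01 and power is lost.
- If allocation was not balanced, the size is near .01 but a similar power gap remains. The Protocol does not say whether allocation was stratified or blocked.

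For R² of .1 to .3, the gain from adjusting at d = .4 is about 5 to 17 points in the balanced simulation. Over all the normal-outcome scenarios it ranges from about 2 points (d = .5, R² = .1) to about 24 points (d = .3, R² = .3). It is 0 to 3 points if the factors are weakly prognostic or only initial drinkers are analysed. The change is worth making. Confidence in its size is medium, because the documents give no variance share or effect.

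**What to change.** Replace the primary test with wording such as:

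> *Peak quantity is compared among the three groups by rank ANCOVA with terms for randomization stratum (Incoming by lifetime drinking, or on campus; each by ALDH2\*2 allele) at p<.01. The unadjusted Kruskal-Wallis test is reported as a sensitivity analysis.*

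If baseline peak quantity was collected, add it as a named covariate; if not, leave it out, so that the model is fixed either way. The calculations above did not include that term. A stratified Kruskal-Wallis test of the van Elteren type is an acceptable alternative without a baseline term; its size in 8,000-run checks was .0084 to .0119.

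State also whether initial non-drinkers are in the primary comparison. If they are not, the lifetime-drinking stratum drops out and little gain is left.

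The cost is plan wording and modest programming. The strata had to be known in order to randomize, and the .01 threshold is unchanged. Rank ANCOVA adds a mild modelling assumption, which the retained Kruskal-Wallis test checks. If outcomes have already been analysed, label the adjusted test as added later.

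A separate, smaller point: the Protocol has four follow-up surveys, and the plan does not say which one carries the primary test. Testing all four at .01 would allow up to about 4% error (1 − .99⁴ = .039). One sentence naming the survey settles it. The final 10-month survey is one candidate, being the only one whose time is stated.

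### The plan does not say which follow-up survey, or what summary of the four, supplies the peak-quantity value for the Kruskal-Wallis test, and it leaves the baseline survey and the randomization factors unused.

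*Combined protocol and SAP*

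**What the plan says.** The Protocol section sets the outcome: "Our alcohol outcome measures include peak quantity (primary) and secondary measures of drinking frequency, weekend drinking, and total amount of drinking". It gives no time point, recall window or summary for any of these measures.

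On timing, it describes a baseline stage ("After a baseline assessment including surveys and DNA collection for genotyping") and then says: "Participants then are followed in four post-intervention behavioral surveys over 10 months". The last survey is singled out only for added content ("in the final 10-month follow-up also complete an evaluation of the study and retention of the intervention information"), not as the time point of the primary outcome.

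On allocation, the 360 participants are split equally into three arms of 120. The Protocol section says that this randomization is "based on lifetime drinking (Incoming cohort only) and having an ALDH2*2 allele".

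The Data Analysis Plan section is a single paragraph. For the drinking measures it says: "For outcomes that are continuous (alcohol consumption measures), we conduct the Kruskal-Wallis test". On error control it says: "We adjust the p-value for significance to a more conservative value of <.01 to adjust for multiple comparisons". It mentions no survey, mean, maximum, change score, baseline covariate, stratification factor or repeated-measures model.

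**The concern.** Kruskal-Wallis compares groups on one independent value per participant and takes no covariates. Four follow-up values must be reduced to one before the test can be run, and the plan does not state the reduction. Two analysts could both follow it faithfully and report different primary results, one from the 10-month survey and the other from a mean or maximum over the year. If that choice is made after the data are seen, the nominal p-value no longer describes the primary claim.

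The second matter is efficiency. Past drinking usually predicts later drinking, and the trial randomizes on two factors likely to be related to drinking. An unadjusted test gives up that information. With the sample fixed at 360, the analysis is the one place where power can be gained without new data.

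**Working it through.** **Inputs from the documents.** 360 participants, 120 per arm (360/3 = 120); four follow-up surveys; six outcomes (peak quantity, three other drinking measures, flush-cure use, transition to drinking); threshold .01. The documents give no effect size, SD, correlation, dropout or power, so there is no planned power figure to reproduce.

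**Assumed inputs.** Constant effect of 0, 0.175 and 0.35 SD in the three arms; the same correlation r between any two surveys, .4 to .7; 20% lost by the last survey; peak quantity recorded at baseline and at every survey.

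**Step 1: variance, relative to one unadjusted survey (= 1).**
- One survey adjusted for baseline: 1 − r². At r = .4, 0.84; at r = .7, 0.51.
- Mean of four follow-ups: (1 + 3r)/4. At r = .4, 0.55; at r = .7, 0.775.
- Mean of four adjusted for baseline: (1 + 3r)/4 − r². At r = .4, 0.55 − 0.16 = 0.39; at r = .7, 0.775 − 0.49 = 0.285.

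**Step 2: power at .01, by simulation.**

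| Analysis | Power, r = .4 to .7 |
|---|---|
| Kruskal-Wallis, 10-month survey | 31–32% |
| Rank ANCOVA with baseline, 10-month survey | 40–64% |
| Kruskal-Wallis, four-survey mean | 55–73% (higher at r = .4) |
| Rank ANCOVA with baseline, four-survey mean | 88–96% |

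Rejection under the null stays near 1%, so the gain is not inflated error.

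**Step 3: check by formula.** The noncentrality is n × Σ(deviation²) × (3/π) / relative variance, with 2 degrees of freedom and critical value 9.21. The sum of squared deviations is 2 × 0.175² = 0.06125.
- Kruskal-Wallis at 10 months, n = 120 × 0.8 = 96: 96 × 0.06125 × 0.955 = 5.61, power 32%.
- Baseline-adjusted mean, r = .4: n = 96 gives 14.4 (82%); n = 120 gives 18.0 (91%).
- Baseline-adjusted mean, r = .7: n = 96 gives 19.7 (94%); n = 120 gives 24.6 (98%).

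The simulated 88–96% lies between these limits. Its exact place depends on when dropout occurs. Spreading dropout evenly, with 5% lost before the first follow-up, gave 83–95%.

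**Step 4: many zeros.** The trial enrolls some non-drinkers. With about half the values at zero, Kruskal-Wallis at 10 months has 20–22% power and the baseline-adjusted mean 72–82%. The evenly spread dropout pattern gave 22–24% and 70–79%.

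**Step 5: a late effect only.** If the effect appears only at the last survey, the four-survey mean has about 2–3% power (3–5% with evenly spread dropout), against about 30% for Kruskal-Wallis at 10 months.

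**Step 6: multiplicity.**
- Peak quantity tested at all four surveys at .01: 1 − .99⁴ = 3.9% if independent, and at most 4 × .01 = 4%.
- Six outcomes at one time point: 1 − .99⁶ = 5.9% if independent.
- Six outcomes at four surveys: 1 − .99²⁴ = 21.4% if independent. With correlation .5–.7 across both outcomes and surveys it is about 11–16%.
- .01 = .05/5, which matches none of 4, 6 or 24 tests.

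**The case against.** The strongest objection is that the plan is silent rather than wrong. A reader might infer that Kruskal-Wallis will be run one survey at a time, so that the primary result must be four tests or a pick of one. The documents do not say so. The test could be applied to a mean, a maximum (a natural reading of a peak measure) or a change from baseline. For the same reason it goes too far to say that the method cannot use the repeated data or throws most of it away. Kruskal-Wallis on the four-survey mean is legitimate and recovers part of the power (55–73%). These points stand, although the extra options widen the unspecified choice. Nor do the documents state that peak quantity is recorded at baseline and at every survey; that is implied.

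A reader might also infer that the .01 rule fails to protect the primary outcome. It does not fail: even four separate tests stay at or below 4%. The 21% figure needs all six outcomes tested at all four surveys and independent. Transition to drinking could equally be one end-of-follow-up event.

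An unadjusted test is valid in a randomized trial, and whether to average over the year or name one survey is partly a choice of question. That is also fair. Naming one survey would cure the selection problem just as well.

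Finally, the protocol calls the study an exploratory pilot. That lowers the stakes. But the plan names a primary outcome and sets a stricter significance threshold, so it intends inference.

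**Conclusion.** The concern holds in limited form. It is certain from the text that the primary test has no named survey or summary, that neither baseline nor the randomization factors enter the analysis, and that the family of tests behind .01 is undefined. The primary result is therefore not fully pre-specified.

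The efficiency loss is likely but conditional. If the 10-month survey is the value tested, adding baseline raises power from about a third to 40–64%. Using the baseline-adjusted four-survey mean raises it to about 88–96% for a constant effect. The size depends on the assumed effect, correlation, dropout and shape of the data. The ordering survives heavy zeros but reverses for an effect confined to the last survey. These figures adjust for baseline only; any gain from the randomization factors is not quantified.

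The sponsor should make this change, but the planned test is not invalid.

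**What to change.** State one primary test of arm on peak quantity: a rank ANCOVA, which stays nonparametric, adjusted for baseline peak quantity and the randomization factors (lifetime drinking in the incoming cohort, ALDH2*2 status). Because lifetime drinking applies to one cohort only, say how it is coded for participants already on campus.

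Name the single value per participant in advance:
- the mean over available follow-up surveys, if the question is the effect across the 10 months; or
- the 10-month survey, if the question is the effect at the end of the study.

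Report the other survey-specific arm estimates as descriptive. Use the same form for the three secondary drinking measures. Confirm that peak quantity is collected at baseline and at each survey, and list the tests that the .01 threshold covers.

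The cost is a paragraph of plan text and modest programming, with no new data if baseline peak quantity is already collected. The mean has two drawbacks. It dilutes an effect seen only at the last survey. Under dropout it also mixes time points between participants, which can bias the comparison if drinking changes over the year and dropout differs by arm. The descriptive estimates would help to show the first; dropout by arm and survey should be reported for the second.
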